In a safety and efficacy study (MDS-001) investigating erythroid response to lenalidomide monotherapy in 43 patients with MDS, lenalidomide yielded a high frequency of major erythroid response (MER) in patients that had either failed prior treatment with erythropoietin or had high endogenous levels and high transfusion burden (6). Patients received treatment with one of three lenalidomide dose schedules, 25 or 10 mg daily, or 10 mg/day x 21 days every 4 weeks. Neutropenia (67%) and thrombocytopenia (57%) > grade 3 NCI-CTC version 2.0 were dose limiting, necessitating treatment interruption and dose-reduction in 25 (61%) patients. Other adverse effects were infrequent and of mild to moderate severity including pruritus, fatigue, diarrhea, edema, thyroid dysfunction and joint discomfort. Among the 36 patients completing more than one cycle of treatment, 24 (67%) experienced an erythroid response according to International Working Group (IWG) criteria (10). MER defined by sustained transfusion-independence (> 8 weeks) or a rise in hemoglobin >2 g/dl was achieved in 21 patients and 3 patients experienced a >50% reduction in red blood cell (RBC) transfusions. Response rate was highest among evaluable patients with a chromosome 5q31.1 deletion (91%) compared to those with a normal karyotype (68%) or other chromosome abnormality (17%) [P=0.009], and response rate was higher in patients with lower (Low-/Intermediate-1) International Prognostic Scoring System (IPSS) risk categories (72% vs. 25%) [P=0.098] (11). Eleven of 17 (65%) patients with karyotypic abnormalities had a 50% or greater reduction in abnormal metaphases, including ten (57%) complete cytogenetic remissions. After a median follow-up of 109 weeks in November

2004, median duration of transfusion-independence had not been reached (81+; range, 19 to > 128 weeks) with a median sustained hemoglobin (Hgb) of 13.4 g/dL (range, 11.5-15.8 g/dL) and median Hgb rise of 5.6 g/dL. The results of this study indicate that lenalidomide has significant and sustained erythropoietic and cytogenetic remitting activity in patients with Low/Intermediate-1 IPSS risk MDS that have failed or are unlikely to benefit from conventional cytokine therapy.

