3.1 Eligibility Criteria

NOTE: Results of the bone marrow biopsy and aspirate as well as Cytogenetics are mandatory to register subjects onto study, which are indispensable to determine IPSS category needed for eligibility (see Section [3.1.1.3](#)). Please note that it is not necessary to wait for the week 16, week 32, or week bone marrow and cytogenetic results prior to starting the next cycle unless deemed necessary by the treating physician. One example of this exception can include if the subject shows signs of progression, such as increased peripheral blood blast percentage. At that juncture, the treating physician may prefer to await the results prior to starting a new cycle. If a cycle is started, and based on the bone marrow results it is felt by the treating physician that the subject should not continue on treatment, please be sure to note this information on the case report forms at end of treatment

____ 3.1.1 **Step 1: Randomization to Arm A or Arm B**

____ 3.1.1.1 Age \geq 18 years.

____ 3.1.1.2 Patient must have documented diagnosis of MDS lasting at least three months (MDS duration \geq 3 months) according to World Health Organization (WHO) criteria (see [Appendix](#)) or non-proliferative chronic myelomonocytic leukemia (CMML) (WBC < 12,000/mcL).

____ 3.1.1.3 Patient must have International Prognostic Scoring System (IPSS) categories of Low- or Intermediate-1-risk disease (see Section [6](#)). Patients must have IPSS score determined by cytogenetic analysis prior to randomization.

Patients must have cytogenetic analysis done (to calculate IPSS). If the current bone marrow biopsy is a dry tap, patients with cytogenetic failure and < 10% marrow blasts will be eligible. Subjects with cytogenetic failure must have previous cytogenetic results (FISH is not a substitute) within the last 6 months post last type of MDS treatment (in this case, not referring to growth factors as type of MDS treatment).

IPSS score: _____ Date of test: _____

Rev. 10/09

_____ 3.1.1.4

Patients must have symptomatic anemia untransfused with hemoglobin < 9.5 g/dL ≤ 8 weeks prior to randomization or with RBC transfusion-dependence (i.e., ≥ 2 units/month) confirmed for ≤ 8 weeks before randomization.

Rev. 10/09

NOTE: For non-transfusion dependent patients (i.e., receiving < 2 units/4 weeks x 8 weeks pre-study) who receive periodic transfusions, the mean 8 week pre-transfusion hemoglobin should be used to determine protocol eligibility and response reference.

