The overall goal of this study is to improve the rate of MER through combined therapy of lenalidomide and epoetin alfa (arm B) by 20% over that of arm A of lenalidomide monotherapy, in which the rate of MER is estimated at 30%, in an MDS population without chromosome 5q31.1 deletion. The anticipated improvement in response is based upon the potentiation of erythroid colony-forming capacity in cell line models. MER will be evaluated at 16 weeks after start of study treatment. Patients without 5q31.1 deletion will be randomly assigned to one of two treatment arms, stratified by serum erythropoietin level (≤ 500 mU/mL vs. > 500 mU/mL) and prior erythropoietin/DA treatment (yes vs. no). Patients with 5q31.1 deletion will be assigned to arm A only for correlative studies, and will not be included in the comparative analysis of the study. The original design required 236 total patients (212 to be randomized) in order to obtain 80% power for the primary comparison. Due to an interruption in drug supply, the study was suspended and epoetin alfa treatment was held on September 24, 2010. At that time, 67 patients were enrolled. Among them, 57 were randomized (29 on arm A, 28 on arm B). 7 patients on Arm B were still within 16 weeks treatment. New supply of epoetin alfa was available for arm B patients on October 27, 2010 and the study was reopened on February 4, 2011. Due to this unexpected drug supply issue, the comparison of the primary endpoint may lose some power. To minimize the potential effect on the primary endpoint, in the revised design, 14 patients (7 on arm A; 7 on arm B) randomized between May 19, 2010 and September 24, 2010 will be excluded from the primary analysis. The total accrual will be increased to 252 (226 to be randomized). This revised statistical considerations section is to incorporate this change.

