9.1 Accrual

This study requires 212 patients (226 to be randomized) without 5q31.1 deletion for the primary endpoint comparison. Assuming that 10% of patients in the MDS population as defined in this study have the 5q31.1 deletion, a total of 252 patients will be entered. Accrual for E1996, a previous study in this patient population was lower than expected. However, since the proposed regimens (lenalidomide, lenalidomide + epoetin alfa) are different from the regimen used in E1996 (erythropoietin vs. supportive care) with promising activity in multi-center phase II trials, and this study will be an intergroup study, we anticipate no accrual impediment. In fact, based on the accrual to the study before its suspension, we anticipate that the accrual rate will be approximately 60 patients per year, and thus, the accrual will be completed in approximately five years, taking the suspension time into account. The feasibility of achieving the accrual goal will be monitored closely by the ECOG-ACRIN Data Monitoring Committee (DMC) and the NCI. According to NCI guidelines, if quarter 5-6 accrual (the number of patients enrolled on trial during quarters 5 and 6 after activation) is $\leq 20\%$ of projected rate, then the trial will be closed; If quarter 5-6 accrual is $< 50\%$ and $> 20\%$ of projected rate, then the study team will be given 6 months to improve accrual. If the average accrual rate in quarter 8 is below 50% then the trial will have to be amended to reflect actual accrual.

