9.2 Primary Endpoint

The primary endpoint in this phase III study of previously erythropoietin/DA-treated MDS patients or erythropoietin/DA-naïve patients but with high transfusion frequency or high endogenous erythropoietin level is major erythroid

response (MER), defined as sustained transfusion independence in transfusion-dependent patients or a rise in hemoglobin > 2 g/dL in transfusion-independent patients with anemia for a minimum of eight consecutive weeks. The objective MER will be assessed 16 weeks after start of study treatment. At the time of objective MER assessment, patients who fail to achieve MER on Arm A will be allowed to crossover to Arm B.

When patients were treated with lenalidomide alone in phase II trials, the MER rates were 25%-34% in patients without a chromosome 5q31.1 deletion and 67% with a chromosome 5q31.1 deletion. There is limited clinical information for the combination of lenalidomide with epoetin alfa. In a pilot study involving 40 patients that had failed erythropoietin monotherapy, 5 of 18 patients who received the lenalidomide and epoetin alfa combination treatment achieved an erythroid response after failing to respond to lenalidomide alone, including 3 MER (12). When UT7 erythroid progenitor cells are treated with lenalidomide and in vitro, clonogenic response and STAT5 activation is additive or greater. Thus, we anticipate that MER rate for the combination of lenalidomide with epoetin alfa will be even higher. Based on this information, we hypothesize that the MER rate in Arm A (lenalidomide) will be 30% and anticipate that the MER rate in Arm B (lenalidomide + epoetin alfa) will be at least 50%. Thus the study is designed to detect an improvement of 20% in the MER rate from 30% to 50%, comparing Arm A to Arm B. Using the statistical package EaSt (Cytel Software Corporation, 1993) to account for multiple interim looks in a sequential design for binomial distribution with continuity correction, a sample size of 212 cases will provide approximately 80% power to detect improvement in MER rate with an overall one-sided type I error rate of 0.025. The primary comparison of the MER rates will be performed on all patients randomized before May 19, 2010 and after September 24. The 14 patients (7 on arm A; 7 on arm B) randomized between May 19, 2010 and September 24, 2010 will be excluded. A secondary analysis will include all 226 patients randomized to this study.

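### Pre-randomization karyotype is mandatory and a plausible predictor of response, but the MER comparison does not use it; a stratified test could gain power at almost no cost

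*Combined protocol and SAP*

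**What the plan says.** Section 1.2 gives the MDS-001 response rate by karyotype: 91% with a 5q31.1 deletion, "compared to those with a normal karyotype (68%) or other chromosome abnormality (17%) [P=0.009". The only other predictor reported there is IPSS risk category (72% against 25%, P=0.098).

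Section 3.1.1.3 makes karyotype a condition of entry: "Patients must have cytogenetic analysis done (to calculate IPSS". After cytogenetic failure on a dry tap, an earlier karyotype is required.

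The opening paragraph of Section 9 says that patients without the deletion "will be randomly assigned to one of two treatment arms, stratified by serum erythropoietin level" and by prior erythropoietin or darbepoetin treatment. Section 4.3 lists the same two factors. Karyotype otherwise sends del 5q31.1 patients to Arm A, outside the comparison, and enters the IPSS score. Its relation to response is a secondary objective (Section 2.2.6).

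Section 9.2 says the study is "designed to detect an improvement of 20% in the MER rate from 30% to 50%, comparing Arm A to Arm B". It was sized "in a sequential design for binomial distribution with continuity correction", with 212 patients giving "approximately 80% power to detect improvement in MER rate with an overall one-sided type I error rate of 0.025". It describes the patients in the primary comparison ("The primary comparison of the MER rates will be performed on all patients randomized before May 19, 2010 and after September 24") but does not name the test. Section 9.4 applies the Table 1 boundaries to a standardized comparison of two rates. No stratum or covariate appears in either section.

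**The concern.** Section 9.3 expects 45% of patients to have a cytogenetic abnormality, so karyotype would divide the randomized patients almost in half. If response differs as much between the halves as Section 1.2 suggests, much of the variation in MER is predictable at baseline, and a test that ignores it gives up power.

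Power matters here. Section 9 says that the 2010 interruption in drug supply may cost some power, and the revised design randomizes 14 more patients to protect the comparison. Section 9.1 adds that an earlier study in this population accrued more slowly than expected. Stratifying the test uses data already collected and needs no extra patients.

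**Working it through.** **Inputs.** 106 per arm (212, taken as 1:1), MER 30% and 50%, one-sided 0.025, continuity correction (Sections 9.1 and 9.2). Seven looks from 53 to 212 cases, boundaries 3.2905 to 2.0703 (Section 9.4, Table 1). 45% abnormal (Section 9.3). Section 9.3 appears to apply that share to each randomized arm: 0.45 × 106 = 47.7, and the widest exact 90% interval for 47 patients is 25.6 points, the width stated there.

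**1. The plan's power.** For a single fixed analysis without continuity correction:

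Φ{[0.20 − 1.96·√(2·0.40·0.60/106)] / √((0.21+0.25)/106)} = Φ{(0.2000 − 0.1319)/0.0659} = Φ(1.03) = 85%.

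Subtracting the continuity correction 1/106 = 0.0094 from the numerator gives Φ(0.89) = 81%. Simulating all seven looks and boundaries with the correction (400,000 trials) gives 80.6% power and type I error 0.0165. Without the correction the figures are 84.4% and 0.0253. The stated figure of about 80% is reproduced.

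**2. The evidence on karyotype.** Section 1.2 gives 24 responders among 36 patients. If the karyotype percentages use those 36, the only whole-number split that fits 91%, 68% and 17% is 10/11, 13/19 and 1/6 (11+19+6 = 36; 10+13+1 = 24). The contrast without del 5q is therefore 13/19 against 1/6:

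- odds ratio (13×5)/(6×1) = 10.8;
- standard error of the log odds ratio √(1/13+1/6+1/1+1/5) = 1.20;
- 95% CI 1.03 to 114; Fisher two-sided p = 0.056.

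The rounded percentages give (0.68/0.32)/(0.17/0.83) = 10.4, which is used below. One more responder among the six would give (13×4)/(6×2) = 4.3, p = 0.18.

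**3. Rates within karyotype.** Overall rates are held at 30% and 50%, with an assumed odds ratio of 10.4 in both arms:

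- Arm A: 47.9% normal, 8.1% abnormal (0.55×0.479 + 0.45×0.081 = 0.300).
- Arm B: 73.6% normal, 21.1% abnormal (0.55×0.736 + 0.45×0.211 = 0.500).

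The within-stratum variance sum is 0.55×(0.479×0.521 + 0.736×0.264) + 0.45×(0.081×0.919 + 0.211×0.789) = 0.353, against 0.21 + 0.25 = 0.46 unadjusted. The ratio is 0.767, so 212 stratified patients carry about the information of 212/0.767 = 276 unadjusted ones.

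**4. Power under the plan's design.** Seven looks, Table 1 boundaries, continuity correction. The comparison is unadjusted against Cochran-Mantel-Haenszel (CMH) stratified by karyotype alone. The odds ratios other than 10.4 are assumed.

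| Karyotype odds ratio | Unadjusted | Stratified |
|---|---|---|
| 10.4, both arms | 80.6% | 89.1% |
| 5, both arms | 80.2% | 84.8% |
| 3, both arms | 80.6% | 82.2% |
| 2, both arms | 80.3% | 80.6% |
| 1 (no effect) | 80.3% | 79.8% |
| 10.4, Arm A only | 80.2% | 81.1% |
| 4.3, Arm A only | 80.0% | 79.9% |

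The first five rows use 60,000 trials each (Monte Carlo standard error √(0.8×0.2/60,000) = 0.16 points) and the last two 30,000. With 50% normal karyotype, the share assumed in Section 9.5, an odds ratio of 10.4 gives 80.1% against 89.5%. Type I error at an odds ratio of 10.4 is the same for both tests: 0.016 with the correction, 0.025 without.

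**The case against.** The strongest reply is that nothing is wrong with the plan. Randomization makes the unadjusted comparison valid, its standard error already covers chance imbalance in karyotype, and the stated power reproduces. All of this stands. A reader might infer that the primary test is biased or underpowered; the documents support neither.

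The evidence is also weak, and that too stands. The contrast rests on about 25 patients, about six of them with other abnormalities. A reader might take P=0.009 as proof of a gap among patients without del 5q, but the sentence also includes the del 5q group at 91%, and the reconstructed contrast alone has p = 0.056. A reader might also call karyotype the strongest predictor. Section 1.2 compares it with only one other, and the documents give no karyotype split for the larger MDS-002 study (N=215).

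The endpoint and population differ as well. The percentages count any erythroid response (21 major, 3 transfusion reductions), and at face value they imply 0.55×68% + 0.45×17% = 45% against the planned 30%. MDS-001 also reported response in patients above Intermediate-1 risk, whom this trial excludes. Poor karyotype scores 1.0 on the IPSS, so eligibility may already remove part of the gap.

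Finally, no document reports response by karyotype under the combination, so a common odds ratio in both arms is an assumption. The Arm A only rows show what happens without it. A reader might also set 85% unadjusted against 93% stratified from a fixed analysis without continuity correction; that is not the plan's design.

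These points limit the likely gain. They do not remove the asymmetry between a possible gain of several points and a cost of about half a point.

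**Conclusion.** The point holds as a recommended efficiency improvement. A mandatory baseline variable with a plausible link to response is left out of the primary and interim MER comparisons. Under the plan's design, stratifying by it raises power from about 80% to about 89% at best, 85% at an odds ratio of 5 and 82% at 3. At 2 the gain is negligible (about 81%). If karyotype matters only in Arm A the change is between nil and about one point, and if it does not matter at all the loss is about half a point. Type I error is unchanged.

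These figures assume 45% abnormal, overall rates of 30% and 50%, and, except in the Arm A only rows, the same odds ratio in both arms. They are for stratification by karyotype alone; adding the two randomization factors was not simulated. The true odds ratio is very uncertain, so 89% is an upper scenario and not a forecast.

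**What to change.** In Sections 9.2 and 9.4, name the primary test as a CMH test of MER, or an equivalent covariate-adjusted test. It should use karyotype together with the two randomization factors, serum erythropoietin level and prior erythropoietin or darbepoetin. Define karyotype as normal or abnormal from the local pre-randomization report, or from the earlier qualifying karyotype after cytogenetic failure. Keep the Table 1 boundaries and report the adjusted risk difference.

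Three binary factors give eight strata, and the first look has 53 cases (53/8 = 6.6 per stratum). The plan therefore needs a stated rule for collapsing sparse strata at early looks.

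Timing decides the status of the change. Section 9.7 gives the study statistician access to interim outcome data, Section 9.4 anticipated analyses from about 2.5 to 5.5 years after active accrual began, and this version carries a safety table dated June 2019. The test must be fixed by people without access to unblinded outcomes. If comparative interim results have already informed those choosing it, make the adjusted analysis a prespecified supportive one and leave the primary comparison unadjusted.

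The cost is a change of wording, the collapsing rule, and about half a point of power if karyotype proves unrelated to response.

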9.3 Secondary Objectives

All analyses on secondary endpoints will be performed on 212 patients randomized before May 19, 2010 and after September 24. The 14 patients (7 on arm A; 7 on arm B) randomized between May 19, 2010 and September 24, 2010 will be excluded.

Time to MER is defined in responders as the time from randomization to the documented date of MER. For transfusion independent patients, the date of MER is the first date of the elevation in hemoglobin level of more than 2 g/dL that has been sustained for at least 8 weeks. For transfusion dependent patients, the date of MER is the beginning date of the time interval of transfusion independence that has been sustained for at least eight weeks.

Time to MER will be compared between lenalidomide monotherapy and combined treatment of lenalidomide and epoetin alfa in MER responders, using a one-sided log-rank test at the significance level of 0.025. Data from a prior study, MDS-001, of patients with MDS show that the median to MER is 11.5 weeks for patients on the lenalidomide schedule of 10 mg/day for 21 days (10). Under the assumption that the proportions of major erythroid responders are 30% for the monotherapy and 50% for the combined therapy, the log-rank test will have 80% power to detect a hazard ratio of 1.88 of the combined therapy over the

monotherapy. If time to MER follows an exponential distribution, this difference corresponds to an improvement in median time to MER from 11.5 weeks to 6.1 weeks.

Duration of MER response is defined as the time interval between the documented date of MER and the earliest date of resumption of RBC transfusions ≥ 2 units in an 8 week period, a reduction in hemoglobin concentration ≥ 2 g/dL in the absence of acute infection, gastrointestinal bleeding and hemolysis, or death.

Duration of MER response will be summarized by Kaplan-Meier method for patients who achieve MER by treatment arms. A secondary analysis will be done on duration of MER response by excluding all patients on arm B whose epoetin alfa treatment was interrupted by the drug supply issue occurred in September 2010.

The 90% confidence interval of the rate of MER to salvage combination therapy will be computed in patients who fail to achieve an MER with lenalidomide monotherapy and cross over to the combination therapy. Since it is assumed that the MER rate on the monotherapy arm is 30%, 74 patients from the monotherapy arm will fail to achieve MER. If among them 60 patients cross over to the combination therapy arm, the 90% confidence interval of the MER rate of the 60 patients will be no wider than 22.5%. A secondary analysis will be done on the rate of MER to salvage combination therapy by excluding those cross over patients whose epoetin alfa treatment was interrupted by the drug supply issue occurred in September 2010.

The minor erythroid response rate will be compared between treatment arms by Fisher's exact test. In a prior study MDS-001 of patients with MDS, 2 minor erythroid responses were observed from 17 patients who were on the lenalidomide schedule of 10 mg/day for 21 days (10). If the minor erythroid response rate is 10% for the monotherapy arm and 30% for the combination therapy arm, there is 94% power to detect this difference at a two-sided significance level 0.05.

Cytogenetic response rate will be calculated by treatment arm among patients with cytogenetic abnormalities, along with its 90% confidence interval. If 45% of patients are expected to have genetic abnormalities, the 90% confidence interval of the response rate is no wider than 25.6% for each arm.

Bone marrow response (CR+PR) rate and its 90% Confidence Interval will be calculated by treatment arm. The 90% Confidence Interval of the bone marrow response rate is no wider than 16.8% for each arm.

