5.5.4 Dose Modifications for Thrombocytopenia

Some MDS patients may develop thrombocytopenia precipitously within the first month of lenalidomide therapy. Therefore, weekly CBCs are assessed during the first eight weeks of the study.

The following are dose interruption/modification guidelines for subjects who develop thrombocytopenia.

5.5.4.1 **For patients with a baseline platelet count
≥ 100,000/mcL;**

5.5.4.1.1 Hold lenalidomide when the platelet count falls to < 30,000/mcL. Lenalidomide should be resumed within eight weeks at the next dose reduction step when the platelet count recovers to ≥ 50,000/mcL. Subsequent cycles should continue at that dose reduction level.

Patients who do not experience platelet recovery within 8 weeks should be removed from study treatment and complete all off-study evaluations.

5.5.4.2 **For patients with a baseline platelet count
<100,000/mcL;**

5.5.4.2.1 Hold lenalidomide for decline in the platelet count ≥ 50% of the baseline value. Lenalidomide treatment should be resumed at the next dose reduction step upon platelet count recovery to ≥ 50,000/mcL. Subsequent cycles should continue at that dose reduction level.

Patients who do not experience platelet recovery within 8 weeks should be removed from study treatment and complete all off-study evaluations.

Baseline plt count	Hold for counts of	Must recover to*
≥ 100,000	< 30,000	≥ 50,000
≥ 60,000 – 99,999	50% of baseline	≥ 50,000
< 60,000	50% of baseline	> 30,000

* Then dose reduce for remainder of cycle. Maintain dose reduction for next cycles, as long as subject meets requirements to start next cycle.

5.5.5 Combined Treatment (Arm B): If, at any time, the Hgb level rises to > 12g/dL, regardless of Hgb rate of rise, the epoetin alfa dose will be withheld until the Hgb level decreases to < 11 g/dL and will be resumed at a decreased dose, as outlined below:

- Epoetin alfa 60,000 U sc QW → 40,000 U sc QW
- Epoetin alfa 40,000 U sc QW → 30,000 U sc QW
- Epoetin alfa 30,000 U sc QW → 20,000 U sc QW
- Epoetin alfa 20,000 U sc QW → 10,000 U sc QW

NOTE: If the Hgb rises due to a transfusion, epoetin alfa will continue to be administered, and the dose level will not change.

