If Hgb rate of rise is > 1 g/dL in the 1-week or 2-week period immediately preceding the next epoetin alfa dose or the Hgb level exceeds 11.5 g/dL (and the Hgb is ≤ 12 g/dL), the epoetin alfa dose will be decreased immediately, as described, but will not be withheld. For example, at the week 5 scheduled dosing visit, assess Hgb rate of rise between weeks 4 and 5 and weeks 3 and 5.

NOTE: Dose re-escalation may be allowed in the event of an increased, and then decreased, Hgb. Follow the recommendations for Epoetin alfa adjustment when reinstituted for decline in Hgb.

Rev. 6/11

5.5.6 Lenalidomide Monotherapy (Arm A): For those patients experiencing a rise in hemoglobin ≥ 14 g/dL on Arm A, lenalidomide should be withheld until the hemoglobin is ≤ 12 g/dL, at which time treatment can be resumed according to the dose adjustment recommendations in Table 1 of Section [5.5.2](#). For those patients previously adjusted to the lowest lenalidomide dose, the lenalidomide schedule should be changed to a 2 week treatment schedule every 4 weeks.

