6.1.2.3 Hematologic Improvement

Improvements must last ≥ 8 consecutive weeks.

1. Erythroid Response

- **Major Erythroid Response:** Transfusion-independence for ≥ 8 consecutive weeks for patients who were RBC transfusion-dependent at baseline AND a ≥ 1 g/dL hemoglobin rise compared to mean pre-transfusion baseline value; or a > 2 g/dL rise in hemoglobin without transfusion for non-transfusion dependent patients.
- **Minor Erythroid Response:** The mean hemoglobin is sustained 1.0 to 2.0 g/dL above the baseline value for a minimum of 8 weeks; or a 50% or greater decrease in 8-week RBC transfusion requirements compared to baseline.

2. Platelet Response

- **Major Platelet Response:** For patients with a pretreatment count $< 100,000/\text{mm}^3$, an absolute increase of $\geq 30,000/\text{mm}^3$; for platelet transfusion-dependent patients, stabilization of platelet counts and platelet transfusion independence.
- **Minor Platelet Response:** For patients with a pretreatment platelet count $< 100,000/\text{mm}^3$, a $> 50\%$ increase in platelet count with a net increase $> 10,000/\text{mm}^3$ but $< 30,000/\text{mm}^3$.

Rev. 6/11

3. Neutrophil Response

- Major Neutrophil Response: For pretreatment ANC < 1500/mm³, ≥ 100% increase, or an absolute increase of ≥ 500/mm³, whichever is greater.
- Minor Neutrophil Response: For ANC > 1500/mm³ before therapy, ANC increase of at least 100%, but absolute increase less than 500/mm³, lasting greater than 8 weeks (56 days).

Rev. 10/09

4. Progression/Relapse Following Erythroid Hematologic Improvement

- For patients who achieve RBC transfusion independence: requirement for ≥ 2 units RBC transfusion in an 8 week period or a reduction in hemoglobin concentration by ≥ to 2 g/dL in the absence of acute infection, gastrointestinal bleeding, hemolysis, etc., reaching a hemoglobin < 9.5 g/dL.
- For patients who achieve ≥ 50% decrease in RBC transfusions: return to pre-treatment RBC transfusion requirement over an 8 week period.

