6.1.2.4 Duration of Response

Time to disease progression (as per Bone Marrow Responses above) or progression/relapse following hematologic improvement (as per Hematologic Improvement above).

7. Study Parameters

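### Section 9.3 defines duration of MER differently from Section 6: it has no hemoglobin floor, no allowance for treatment holds, a different event list and no stated reference value

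*Combined protocol and SAP*

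**What the plan says.** Section 9.3 starts duration of MER at the documented MER date. It ends it at the earliest of three events: resumed transfusion of at least 2 units in 8 weeks, a hemoglobin fall of at least 2 "g/dL in the absence of acute infection, gastrointestinal bleeding and hemolysis, or death". The durations are then summarized by Kaplan-Meier in each arm. No test, significance level or power is given.

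Section 6.1.2.3 item 4 defines relapse after erythroid improvement. It has the same transfusion trigger and the same 2 g/dL fall, but its exceptions end with "gastrointestinal bleeding, hemolysis, etc., reaching a hemoglobin < 9.5 g/dL". Section 6.1.2.4 defines duration of response as "Time to disease progression (as per Bone Marrow Responses above) or progression/relapse following hematologic improvement", and so takes over the 9.5 g/dL condition. The relapse rule after CR or PR in Section 6.1.2.1 names an interruption of treatment among its exceptions; Section 9.3 does not.

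Two dosing rules lower hemoglobin on purpose. In Section 5.5.6 (Arm A), once hemoglobin is 14 g/dL or more, "lenalidomide should be withheld until the hemoglobin is" 12 g/dL or less. In Section 5.5.5 (Arm B), once hemoglobin is above 12 g/dL, "the epoetin alfa dose will be withheld until the Hgb level decreases to < 11 g/dL".

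**The concern.** One endpoint has two definitions, and an analysis program cannot follow both. The Section 9.3 version has no floor and no exception for a hold. A patient whose drug was stopped because hemoglobin was high, and whose hemoglobin then came down to 12 g/dL as the protocol intends, could be recorded as having lost the response while still a responder under Section 6.

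Duration of MER by treatment assignment is a named secondary objective (2.2.2). The hold rules differ between the arms in drug, trigger and resumption level, so the definition could act unequally on the two Kaplan-Meier curves. If the choice between definitions is left until the data are in hand, it becomes a post hoc choice.

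**Working it through.** The plan gives no event count, power or precision for duration of MER, so there is no figure to reproduce. The check compares the two definitions and then applies threshold arithmetic.

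**1. The definitions side by side**

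| Element | Section 9.3 | Sections 6.1.2.3 item 4 and 6.1.2.4 |
|---|---|---|
| Transfusion trigger | at least 2 units in 8 weeks | same |
| Hemoglobin trigger | fall of at least 2 g/dL | fall of at least 2 g/dL and below 9.5 g/dL |
| Exceptions | three, closed list | the same three, list left open |
| Death | event | not listed |
| Disease progression | not listed | event |
| Reference for the fall | not stated | not stated |

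**2. Direction of the floor omission.** For a given reference value, any fall that meets the Section 6 hemoglobin rule also meets the Section 9.3 rule, but not the reverse. Dropping the floor can therefore only add hemoglobin events or move them earlier. The missing progression event works the other way: a responder who progresses or transforms to AML stops treatment (5.7.5) but has no Section 9.3 event.

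**3. Arm A hold, fall measured from peak.** Minimum fall = trigger − resumption level = 14 − 12 = 2.0 g/dL. A peak of 15 gives at least 3.0, and a peak of 15.8 at least 3.8. Every completed hold meets the Section 9.3 criterion. At 12 g/dL none meets the Section 6 criterion, because 12 is above 9.5.

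**4. Arm B hold, fall measured from peak.** The thresholds imply a fall of only just over 12 − 11 = 1 g/dL. With resumption at 10.9 g/dL:

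| Peak (g/dL) | Fall to 10.9 | Section 9.3 event? | Section 6 event? |
|---|---|---|---|
| 12.1 | 1.2 | no | no |
| 12.5 | 1.6 | no | no |
| 12.9 | 2.0 | yes | no |
| 13.4 | 2.5 | yes | no |

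A completed Arm B hold therefore ends the MER at resumption only after a peak of about 13 g/dL or more.

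**5. Fall measured from hemoglobin at the MER date.** A fall to 12 is an event only if hemoglobin was already 12 + 2 = 14 or more at that date. A fall to 10.9 needs 10.9 + 2 = 12.9 or more. Untransfused patients enter below 9.5 g/dL (3.1.1.4), and their MER date is the first rise of more than 2 g/dL. Hemoglobin on that date will often be near or below 9.5 + 2 = 11.5, and a 2 g/dL fall from 11.5 lands at 9.5. On this reading the two definitions nearly coincide for such patients.

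**6. With the Section 6 floor restored.** Arm A resumes at 12, which is 12 − 9.5 = 2.5 g/dL above the floor. Arm B resumes just under 11, about 11 − 9.5 = 1.5 g/dL above it. Neither hold scores at its resumption level under either reference.

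**7. Scale.** At the design rates of 30% and 50% with 212 / 2 = 106 patients per arm, responders number about 0.30 × 106 = 32 and 0.50 × 106 = 53. Before censoring, one reclassified patient moves the Arm A curve by 1/32 = 3.1 percentage points and the Arm B curve by 1/53 = 1.9. The number reclassified cannot be derived, because the documents give no frequency of holds or of overshoot.

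**The case against.** The strongest reply is that the hold problem depends on a reference value that Section 9.3 never gives. Measured from the MER date, as step 5 shows, most holds would not count. This stands, and it limits the claim to a conditional one. It also exposes a further gap, since Section 9.3 cannot be programmed without a reference.

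Second, a reader might infer that the protocol forces a recorded relapse in its best responders in both arms. The documents do not support that. A hold lasts until a level is reached and does not guarantee that it will be. Arm B thresholds alone imply only just over 1 g/dL, and Section 5.5.5 cuts the epoetin dose once hemoglobin exceeds 11.5 g/dL or rises by more than 1 g/dL in one or two weeks, which limits overshoot. Overshoot remains possible, because blood counts become two-weekly and then four-weekly (Section 7.1, footnote 10).

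Third, a reader might turn the MDS-001 responders' hemoglobin in Section 1.2 (median 13.4, range 11.5 to 15.8 g/dL) into a share of Arm A patients reaching 14. Those figures show only that 14 lies within an observed range. That study included del(5q) patients, who are outside this trial's comparison, and other dose schedules, and no distribution is given.

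Fourth, Section 9 could be read as shorthand for Section 6. Section 7.1 does send response assessment to Section 6.1.2, and Section 9.2 also omits part of the MER definition. But Section 9.3 adds death and leaves out progression, so it is a different rule and not an abbreviation.

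**Conclusion.** The conflict between Section 9.3 and Sections 6.1.2.3 and 6.1.2.4 is established by the text. It covers the 9.5 g/dL floor, the exceptions, and the treatment of death and progression. It is also certain that, for a common reference value, omitting the floor can only add hemoglobin events or bring them forward.

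The effect of the holds is conditional. Measured from peak, all completed Arm A holds count as loss of MER, and so do Arm B holds after a peak of about 13 g/dL or more. Measured from the MER date, far fewer do. The two curves could be affected unequally, but a reader should not infer a bias in favor of either arm: net size and direction cannot be computed, and the missing progression event pulls the opposite way.

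Objective 2.2.2 is to evaluate duration, and the planned analysis is descriptive. The primary MER comparison, its type I error, its power and the interim boundaries are unaffected. This is a correction to a secondary endpoint that should be settled before the durations are analyzed.

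**What to change.** Reconcile Section 9.3 with Sections 6.1.2.3 and 6.1.2.4:

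- Use the Section 6 hemoglobin criterion (a fall of at least 2 g/dL that reaches below 9.5 g/dL) in the duration analysis. Apply it explicitly to all MER patients, since item 4 is worded for those who achieve transfusion independence or a reduction in transfusions.
- State the reference hemoglobin from which the fall is measured.
- State that a fall during a protocol-required hold for high hemoglobin is not an event in itself.
- Use one event list in both sections, and say how disease progression or AML and death are counted.

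The cost is a few lines in Sections 9.3 and 6.1.2.4 (and item 4 if its wording is extended). No new assessments or data are needed, and no change to any dosing or hold rule is proposed.
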